8.3.2 MECHANISM

Body Image Coping Strategies Inventory. The BICSI is a 29-item, validated measure of the cognitive and behavioral responses to manage threats to body image.⁵⁵ BICSI contains three sub-domains; (1) appearance fixing (altering appearance by covering, camouflaging, or correcting the perceived defect), (2) avoidance (an attempt to escape or avert stressful body-image situations), and (3) positive rational acceptance (acceptance of the challenging event and positive self-care or rational self-talk about one's appearance). Items are scored on a 4-point Likert scale from 'Definitely not like me' (0) to 'Definitely like me' (3). The score for each subscale is calculated by summing the values for the individual questions and thus ranges as follows: Appearance fixing (0-30), Avoidance (0-24), and Positive rational acceptance (0-33). For each subscale, higher scores indicate greater reliance on that type of body image coping strategy.

Automatic Thoughts Questionnaire. The Automatic Thoughts Questionnaire is a 15-item, validated, patient-reported measure of negative automatic thoughts.⁹⁶ Items are scored using a 5-point Likert scale (1-5). The total score is calculated by summing the individual responses. Total scores range from 15-75; higher scores reflect more negative automatic thoughts.

Working Alliance Inventory-Short Revised-Therapist. The Working Alliance Inventory Short Revised-Therapist Version is a 10-item, validated, assessment of the strength of alliance (bond, goals, task) between the therapist and client, as rated by the therapist.⁷⁶ Items are scored using a 5-point Likert scale from 'Seldom' (1) to 'Always' (5). The total score is calculated by summing the individual responses. The total score ranges from 10-50; higher scores reflect stronger alliance (bond, goal, task) between the therapist and the client as rated by the therapist.

Therapist Empathy Scale. The Therapist Empathy Scale is a 9-item validated measure of therapist empathy as rated by a 3rd party observer.⁹⁷ Items are scored using a 7-point Likert scale from 1-7. The total score is calculated by summing the individual responses and thus ranges from 9-63. Higher scores reflect more frequent empathy by the therapist.

Credibility/Expectancy Questionnaire-Expectancy Subscale. The Credibility/Expectancy Questionnaire-Expectancy Subscale is a 3-item, validated assessment of the patient's expectations for improvement with the intervention.⁹⁸ Items are scored using a 9-point Likert scale from 1-9. The total score is calculated by summing the individual responses and thus ranges from 3-27. Higher scores reflect greater expectation of improvement from the intervention.

8.3.3 INTERVENTION FIDELITY

BRIGHT Fidelity and Competence Scale. The BRIGHT Fidelity and Competence Scale is a system for rating the fidelity and skill level of therapists delivering BRIGHT that consists of 11 items grouped in 3 subscales: Assessment (1 item), General (4 items), and BRIGHT (6 items). All of the items use a common Likert-type scale from 1-7. For each item, two dimensions are rated using this Likert scale. The first dimension, 'Frequency and Extensiveness', is a 'quantity' or 'fidelity' rating that taps the degree to which

the intervention was present in that session (e.g., whether it occurred and with what intensity). The second dimension, 'Skill Level', is a 'quality' or 'competence' rating that indicates skill with which the therapist delivered the intervention (and is rated only if the intervention occurred within the rated session). 'Frequency and Extensiveness' is rated on a Likert scale of 1-7 (not at all to extensively) with higher scores reflecting greater frequency and extensiveness of the item. 'Skill level' is rated from 1-7 (very poor to excellent) with higher scores reflecting greater skill on each item. The BRIGHT Fidelity and Competence Scale is modeled from the Yale Adherence and Competence Scale (YACS), a validated scale for rating therapist adherence and competence in delivering behavioral treatments for substance use disorders.⁸⁶ Details for scoring and interpreting the BRIGHT Fidelity and Competence Scale are provided in its accompanying Rater Manual.

Interventionist Self-Report. The Interventionist Self-Report is a self-report checklist (yes/no) mapped to agenda content for each of the 6 sessions for BRIGHT or AC.

8.3.4 PARTICIPANT ADHERENCE

Adherence will be assessed with the following measures: (1) attendance at intervention visits; (2) duration of study visits; (3) homework completion (for BRIGHT); (4) interventionist rating of patient engagement and material comprehension.

8.4 ADVERSE EVENTS AND SERIOUS ADVERSE EVENTS

8.4.1 DEFINITION OF ADVERSE EVENTS

This trial is considered to carry a low risk to subjects (i.e. has a "no more than minimal risk" designation). As such, this protocol defines an adverse event (AE) as any sustained undesirable psychological, social, or emotional reaction that is definitely, probably, or possibly related to the study intervention. AEs include suicide attempt, sustained emotional distress, sustained depression, or other sustained mental health deterioration. This definition of an adverse event follows best practices for recording adverse events during psychological treatments.⁹⁹

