2.3 RISK/BENEFIT ASSESSMENT

2.3.1 KNOWN POTENTIAL RISKS

Overall, this research study poses no more than minimal risks to participants. The single-arm pilot study of BRIGHT and single-site pilot RCT comparing BRIGHT with AC were minimal risk studies that were approved by the Medical University of South Carolina (MUSC) Institutional Review Board (IRB) under an expedited review (45CFR46.110). The proposed study will use a single IRB structure with MUSC serving as the IRB of record. No formal Data and Safety Monitoring Board was required in the prior studies of BRIGHT, although a Data and Safety Monitoring Plan (DSMP) with principal investigator (PI) and IRB-based oversight was created. The main study procedures include (1) either BRIGHT (CBT) or AC (a manualized tele-supportive care intervention that controls for professional attention, dose, delivery method, and common factors) and (2) completion of study questionnaires. These are generally considered minimal risk activities, although one of the questionnaires inquires about suicidal ideation. There are no physical, financial, legal, social, or cultural, risks to the study participants by joining this study. The primary risks of the study associated with the intervention or study assessments include psychological/emotional distress and breach of privacy/confidentiality.

Psychological/emotional distress: Subjects may experience adverse psychological reactions such as anxiety, depression, stress, distress, or suicidal ideation as a result of discussing issues related to cancer, body image, stigmatization, isolation, coping strategies, or social support. These issues may occur during the completion of study questionnaires (baseline or post-treatment) or during the intervention (BRIGHT or AC). However, based on our experience with prior similar trials, we expect only minimal risk to participants. Nevertheless, we have a specific protocol to address situations in which a patient becomes distressed as a result of either the study intervention or study assessments. The project coordinator and all of the study interventionists have extensive experience dealing with this patient population and appropriate safeguards have been put in place to mitigate against this risk in either situation. There is a licensed clinical psychologist at each site that is trained in assessing and intervening upon distress.

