3 OBJECTIVES AND ENDPOINTS

Table 5. Study Objectives and Endpoints	
OBJECTIVES	ENDPOINTS
Primary	
To evaluate the efficacy of BRIGHT compared with AC on HNC-related BID as measured by change from baseline in the IMAGE-HN score.	Change in the IMAGE-HN score from baseline to 6-months follow-up ^a
Secondary	
To evaluate the clinical response rate of BRIGHT compared with AC on HNC-related BID as measured by proportion of patients with a clinically meaningful change from baseline in the IMAGE-HN score.	Proportion of patients with a decrease in the IMAGE-HN score of ≥ 9 points from baseline
To further evaluate the short and longer-term efficacy of BRIGHT compared with AC on HNC-related BID as measured by change from baseline in the IMAGE-HN score.	Change in the IMAGE-HN score from baseline to 2-, 3-, and 9-month follow-up
To evaluate the efficacy of BRIGHT compared with AC on psychological and social well-being as measured by change from baseline in the Shame and Stigma Scale in HNC, PROMIS SF v1.0-Depression 8a, PROMIS SF v1.0-Anxiety 8a, Beck Scale for Suicidal Ideation, and PROMIS SF v2.0-Ability to Participate in Social Activities-8a scores.	Change in the Shame and Stigma in HNC score from baseline to 3-, 6-, and 9-month follow-up
	Change in the PROMIS SF v1.0-Depression 8a score from baseline to 3-, 6-, and 9-month follow-up
	Change in the PROMIS SF v1.0-Anxiety 8a score from baseline to 3-, 6-, and 9-month follow-up
	Change in the Beck Scale for Suicidal Ideation score from baseline to 3-, 6-, and 9-month follow-up
	Change in the PROMIS SF v2.0-Ability to Participate in Social Activities 8a score from baseline to 3-, 6-, and 9-month follow-up
To evaluate the efficacy of BRIGHT compared with AC on QOL as measured by change from baseline in the EORTC QLQ-HN35 score.	Change in the EORTC QLQ-HN35 Trouble with Social Eating and Trouble with Social Contract subscale scores from baseline to 3-, 6-, and 9-month follow-up

Table 5. Study Objectives and Endpoints	
OBJECTIVES	ENDPOINTS
To examine the mechanism of change underlying BRIGHT for HNC-related BID as measured by change from baseline in the Body Image Coping Strategies Inventory (BICSI) subscale scores and Automatic Thoughts Questionnaire scores.	Change in the BICSI Avoidance subscale score from baseline to 2-, 3-, and 6-month follow-up
	Change in the BICSI Positive Rational Acceptance subscale score from baseline to 2-, 3-, and 6-month follow-up

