PROMIS SF v1.0-Anxiety 8a. The PROMIS SF v1.0-Anxiety 8a is an 8-item, validated, developed by the NIH to assess patient-reported fear, worry, and hyperarousal.⁸⁹ Responses rate the strength of agreement with statements about anxiety symptoms using a scale that ranges from 1-5. The total raw score is calculated by summing the individual responses. The PROMIS SF v1.0-Anxiety 8a raw score ranges from 8-40; a higher score reflects more severe anxiety symptoms. The PROMIS SF v1.0-Anxiety 8a total raw score is translated into a T-score for each participant according to the PROMIS Scoring manual. The T-score provides a standardized score with a mean of 50 and a standard deviation of 10.

Beck Scale for Suicidal Ideation. The Beck Scale for Suicidal Ideation is a 21-item, validated, patient-self report rating scale to rate the severity of a patient's suicidal thoughts and plans.⁹⁰ Each item consists of three options graded according to suicidal intensity from 0 to 2. The ratings for the first 19 items are summed to yield a total score, which ranges from 0 to 38. Higher scores represent more severe suicidal ideation.⁹¹ A cutoff score of > 2 is optimal to indicate high/low risk of suicidal ideation.⁹²

PROMIS SF v2.0-Ability to Participate in Social Activities 8a. PROMIS SF v2.0-Ability to Participate in Social Activities 8a is an 8-item, validated, unidimensional measure of patient-reported perceptions of participation in social activities.^{93,94} Items are scored using a 5-point Likert scale from 'Never' (1) to 'Always' (5). The total raw score is calculated by summing the individual responses. The total raw score ranges from 8-40; a higher score reflects more severe inability to participate in social activities. The total raw score is translated into a T-score for each participant according to the PROMIS Scoring manual. The T-score provides a standardized score with a mean of 50 and a standard deviation of 10.

EORTC QLQ-HN35 Trouble with Social Eating Subscale. The EORTC QLQ-HN35 Trouble with Social Eating Subscale is a 4-item, validated measure of trouble with social eating for patients with HNC.⁹⁵ The subscale is composed of QLQ-H&N35 items 19-22. Items are scored using a 4-point Likert scale from 'not at all' (0) to 'very much' (3). The total score is calculated by summing the individual responses. Total subscale scores range from 0-12; higher scores reflect more trouble with social eating.

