8.4.2 DEFINITION OF SERIOUS ADVERSE EVENTS

A serious adverse event (SAE) will be defined as any sustained undesirable psychological or mental health condition which is fatal, is life-threatening, requires or prolongs inpatient hospitalization, results in persistent or significant disability/incapacity, is medically significant and which the investigator regards as serious based on appropriate medical judgment that is directly due to a study intervention. An important medical event is any AE that may not result in death, be life-threatening, or require hospitalization but may be considered an SAE when, based upon appropriate medical judgment, it may jeopardize the patient and may require medical or surgical intervention to prevent one of the outcomes listed in the definitions of SAEs.

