8.4.8 EVENTS OF SPECIAL INTEREST

N/A

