
9.4.4 SAFETY ANALYSES

All patients in the SAS will be evaluated for safety and toxicity. Adverse events, SAEs and will be summarized. Safety analyses will include the following summaries:

- AEs, including severity and relationship to a study intervention
- SAEs, including relationship to a study intervention

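### A suicidal crisis short of an attempt can trigger the protocol's emergency procedures and still be missing from its stated safety comparison

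*Protocol*

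**What the plan says.** Section 2.3.1 of the protocol states the risk: "Subjects may experience adverse psychological reactions such as anxiety, depression, stress, distress, or suicidal ideation". Section 2.3.3 describes the response: a REDCap alert on positive Beck answers, a psychologist's risk assessment, a safety plan for low to moderate risk, and a call to emergency services for imminent risk.

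The recording rules are narrower. Section 8.4.1 defines an adverse event as "any sustained undesirable psychological, social, or emotional reaction that is definitely, probably, or possibly related to the study intervention" and gives examples: "AEs include suicide attempt, sustained emotional distress, sustained depression, or other sustained mental health deterioration". Section 8.4.2 starts the serious adverse event definition with "any sustained undesirable psychological or mental health condition which is fatal, is life-threatening, requires or prolongs inpatient hospitalization" and ends it by requiring that the condition result directly from the intervention. Section 8.4.5 collects and reports events that fit the definition. Section 8.4.8, "EVENTS OF SPECIAL INTEREST", is marked not applicable.

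The safety analyses in 9.4.4 consist of "AEs, including severity and relationship to a study intervention" and the matching summary for serious events. The Beck Scale appears in Table 5 as an efficacy endpoint: "Change in the Beck Scale for Suicidal Ideation score from baseline to 3-, 6-, and 9-month follow-up". Section 8.3.1 also reports a threshold, "A cutoff score of > 2 is optimal to indicate high/low risk of suicidal ideation", which no analysis stated in the protocol uses.

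**The concern.** The protocol treats suicidality as a risk serious enough to need daily alert checks and emergency calls, but nothing in 2.3.3 says that an episode handled this way is recorded as an adverse event or counted. Whether it is counted depends on two case-by-case judgments made beforehand: that it was sustained, and that it was at least possibly related.

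A randomised safety comparison gets its strength from counting events in both arms and letting the comparison speak to cause. If attribution decides what is counted, a real difference between arms in suicidal crises could go unseen. There is also a data-capture problem. A later analysis plan can re-tabulate Beck scores, but it cannot recover safety plans or emergency calls that were never entered as data.

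**Working it through.** The plan states no figure on this point, so the check is mainly a trace of the text.

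**1. Conditions for being counted.**
- Adverse event (8.4.1): sustained, and at least possibly related. Sustained is not defined.
- Serious adverse event (8.4.2): sustained, serious, and directly caused by the intervention. The important-medical-event clause does not widen this, because it covers only events that are already adverse events.
- Relatedness scale (8.4.3.2): definite, probable, possible. There is no unrelated category, which is consistent with unrelated events not being collected.
- By arm: 9.4.4 does not use these words. The grouping follows from 9.3, where the safety set is analysed by intervention received.

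**2. Episodes run through those conditions.**

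| Episode | Adverse event | Serious adverse event | In the 9.4.4 summaries |
|---|---|---|---|
| Attempt, at least possibly related | Yes, listed | Only if 8.4.2 is also met | Yes |
| Attempt, judged below possibly related | No | No | No |
| Crisis without attempt, judged sustained and at least possibly related | Yes | Only if 8.4.2 is also met | Yes |
| Crisis without attempt, related but not judged sustained | No | No | No |
| Crisis without attempt, judged below possibly related | No | No | No |

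Any of the five could have set off the procedures in 2.3.3. Three need not appear in a safety summary.

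**3. Does the Beck endpoint fill the gap?** Table 5 uses change at 3, 6 and 9 months. Section 9.4.3 analyses it in a similar way to the primary endpoint, which is a model for mean change. Section 9.3 restricts it to patients who completed both the baseline and the follow-up survey. The schedule in 1.3 lists the scale at screening and follow-up, not at the treatment sessions. A crisis that resolves before the survey contributes nothing, and a patient who does not complete the survey leaves the analysis.

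*Illustration only.* Inputs: 90 evaluable patients per arm (9.2); score range 0 to 38 (8.3.1); number of crises k and rise d per crisis are assumptions. Shift in arm mean = k × d / 90.
- k = 1, d from 0 to 38: 0 to 38/90 = 0.42 points.
- k = 2, d = 20: 40/90 = 0.44 points. If both start at 0, 2/90 = 2.2% of the arm has crossed the threshold of 2.
- k = 3, d = 10: 30/90 = 0.33 points; d = 38: 114/90 = 1.27 points.

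Different combinations of k and d give similar shifts, so a mean change does not reveal the number of crises.

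**The case against.** The case for leaving the text alone has real substance.

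- **Attempts.** A reader might infer that all suicidality must be sustained to count. The text does not support that: attempt is the one example in 8.4.1 without the qualifier. Only relatedness clearly binds it. This stands, and the point is limited accordingly.
- **Relatedness is a low bar.** Under 8.4.3.2, possibly related needs only some evidence, such as timing, and allows that the patient's condition contributed. A reader might infer that any crisis attributed to the cancer drops out. That is too strong: only one judged below possible does.
- **Sustained is undefined.** It is therefore not proven that a short crisis is excluded. What is shown is that the text permits exclusion and leaves the decision open.
- **Unseen documents.** A table of Beck scores above 2 could be in the analysis plan, and 2.3.3 refers to a data and safety monitoring plan. So it cannot be claimed that suicidality will be analysed only as a mean. The adverse event definition and collection rule, however, are fixed in this protocol.
- **Other oversight.** Section 9.5.7 has the principal investigator review adverse events and endpoint data monthly, and 8.5 covers unanticipated problems. Neither is described as a comparison between arms, and 8.5 also requires possible relatedness.
- **Biased attribution.** A reader might infer that attribution would favour one arm. The protocol does not show this: the principal investigator judges relatedness, and 6.3 says investigators are blinded to allocation.
- **A deliberate choice.** The definition was revised on purpose and cites a source on recording harms in psychological trials. That explains the related-event table, but does not reconcile it with 2.3.1 and 2.3.3.

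**Conclusion.** The concern holds in a limited form. A suicidal crisis short of an attempt is in the stated safety comparison only if judged sustained, an undefined term, and at least possibly related. An attempt is in it only if judged at least possibly related. The planned Beck change score does not count such episodes.

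How many would be lost cannot be derived, because the protocol gives no expected rate of crises, alerts or emergency calls. The Beck arithmetic shows only that a mean is a poor counter; the scores in it are assumed. The conclusion rests on the protocol text and on neither the analysis plan nor the monitoring plan adding a separate count. The defect is worth correcting while data can still be captured. It does not affect the primary analysis.

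**What to change.** Reconcile sections 2.3.1, 2.3.3, 8.4.1, 8.4.2, 8.4.8 and 9.4.4:

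- In 8.4.8, replace the not-applicable entry with suicidality episodes as events of special interest: red flag, safety plan, activation of emergency services, attempt. Record them regardless of duration or attribution.
- In 9.4.4, tabulate these by arm. Add the number of patients with a Beck score above 2, overall and new since baseline, unless the analysis plan already does so.
- Keep the related adverse event table as it is.

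Beck scores and alerts are already in REDCap. The cost is a yes/no field for the safety-plan and emergency-call actions, and one more safety table. No care procedure in 2.3.3 changes.

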8.4.2 DEFINITION OF SERIOUS ADVERSE EVENTS

A serious adverse event (SAE) will be defined as any sustained undesirable psychological or mental health condition which is fatal, is life-threatening, requires or prolongs inpatient hospitalization, results in persistent or significant disability/incapacity, is medically significant and which the investigator regards as serious based on appropriate medical judgment that is directly due to a study intervention. An important medical event is any AE that may not result in death, be life-threatening, or require hospitalization but may be considered an SAE when, based upon appropriate medical judgment, it may jeopardize the patient and may require medical or surgical intervention to prevent one of the outcomes listed in the definitions of SAEs.

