6.3 MEASURES TO MINIMIZE BIAS: RANDOMIZATION AND BLINDING

Bias will be minimized through the randomized permuted block design. Randomization will occur at the individual patient level. Following provision of written informed consent and completion of baseline study assessments, patients will be randomized 1:1 to BRIGHT or AC using a stratified permuted block

randomization design with randomly selected block sizes of 4 or 6 to avoid deterministic treatment allocation. Randomization will be stratified by site (MUSC, HFH, WUSM) and free flap reconstruction (yes/no) to minimize variability in practices or patient characteristics between sites. The random allocation sequence will be generated by the lead study biostatistician using a computer-generated algorithm. The program coordinator will implement the random allocation sequence using the REDCap randomization feature to conceal the sequence until intervention assignment. Randomization errors will be handled as per ITT analyses for the efficacy population.

Study investigators will be blinded to allocation. Outcome assessors are not blinded to allocation, but all study assessments are patient-reported outcomes and thus unlikely to be biased by outcome assessors knowing study allocation. Staff delivering BRIGHT/AC cannot be blinded due to face-to-face intervention delivery. Patients are not blinded but they also are not instructed whether BRIGHT or AC is the active intervention.

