8.4.3.2 RELATIONSHIP TO STUDY INTERVENTION/EXPERIMENTAL MANIPULATION

All AEs will have their relationship to study procedures, including the intervention, assessed by the PI based on temporal relationship and his clinical judgment. The degree of certainty about causality will be graded using the categories below.

- **Definitely Related** – There is clear evidence to suggest a causal relationship, and other possible contributing factors can be ruled out. The clinical event, including an abnormal laboratory test result, occurs in a plausible time relationship to study procedures administration and cannot be explained by concurrent disease or other drugs or chemicals. The response to withdrawal of the study procedures should be clinically plausible. The event must be pharmacologically or phenomenologically definitive.
- **Probably Related** – There is evidence to suggest a causal relationship, and the influence of other factors is unlikely. The clinical event, including an abnormal laboratory test result, occurs within a reasonable time after administration of the study procedures, is unlikely to be attributed to concurrent disease or other drugs or chemicals, and follows a clinically reasonable response on withdrawal.
- **Possibly Related** – There is some evidence to suggest a causal relationship (e.g., the event occurred within a reasonable time after administration of study procedures). However, other factors may have contributed to the event (e.g., the participant's clinical condition, other concomitant events). Although an AE may rate only as "possibly related" soon after discovery, it can be flagged as requiring more information and later be upgraded to "probably related" or "definitely related", as appropriate.

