8.4.4 TIME PERIOD AND FREQUENCY FOR EVENT ASSESSMENT AND FOLLOW-UP

Recording/reporting of AEs will begin after the subject signs informed consent and end after the subject completes the intervention and follow up period as defined in the protocol. AEs may be reported by the patient via self-report, noted in the electronic medical record, or reported directly by study personnel.

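### The AE and SAE definitions cover the study intervention only, leaving out assessment reactions that other sections recognise, and the relatedness threshold for an SAE is unclear

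*Protocol*

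**What the plan says.** Section 8.4.1 of the protocol defines an AE as "any sustained undesirable psychological, social, or emotional reaction that is definitely, probably, or possibly related to the study intervention". Section 8.4.2 lists the usual seriousness criteria and ends the list with "based on appropriate medical judgment that is directly due to a study intervention". It then adds: "An important medical event is any AE that may not result in death, be life-threatening, or require hospitalization but may be considered an SAE". Neither definition mentions assessments or other study procedures. Section 8.4.5 collects and reports AEs as so defined, and section 8.4.6 sends the evaluation of an SAE to the NIH and the reviewing IRB.

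Other sections are wider:

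- Section 2.3.1, on psychological reactions that include suicidal ideation: "These issues may occur during the completion of study questionnaires (baseline or post-treatment) or during the intervention (BRIGHT or AC".
- Section 8.4.3.2: "All AEs will have their relationship to study procedures, including the intervention, assessed by the PI". It offers three grades: definite, probable and possible.
- Section 8.4.4: "Recording/reporting of AEs will begin after the subject signs informed consent".
- Section 6.3: "Following provision of written informed consent and completion of baseline study assessments, patients will be randomized 1:1". The baseline questionnaires therefore come before any session.

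Section 9.4.4 plans to summarise both AEs and SAEs by relationship to a study intervention.

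**The concern.** There are two mismatches.

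The first is scope. The risk section, the causality section and the recording window all reach beyond the intervention, but the two definitions that decide what is counted do not. A harm that the protocol itself foresees, a sustained reaction to a questionnaire, has no place in the AE or SAE record if the definitions are followed as written.

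The second is threshold. An AE need only be possibly related. An SAE is tied to a phrase that is not one of the protocol's relatedness grades and whose place in the sentence is uncertain. The person classifying a hospitalisation judged possibly related cannot tell from the text whether it is an SAE.

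The stake is safety reporting, not efficacy. Sections 2.1 and 2.2.2 describe suicide mortality in these survivors as 2-fold that of other cancer survivors and 4-fold that of the general population. The SAE label is what triggers the section 8.4.6 report.

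**Working it through.** There is no figure in the plan to reproduce, and the point does not depend on power or alpha. The check is a comparison of texts.

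**Scope**

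| Section | Subject | Reach |
|---|---|---|
| 2.3.1 | Foreseen harm | Questionnaires (baseline and later) and sessions |
| 8.4.1 | AE definition | Study intervention |
| 8.4.2 | SAE definition | Study intervention |
| 8.4.3.2 | Causality grading | Study procedures, with the intervention as one part |
| 8.4.4 | Recording window | From signed consent |
| 9.4.4 | Safety summaries | Study intervention |

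1. Section 6.3 fixes the order as consent, baseline assessments, randomization. Sessions follow.
2. Section 8.4.4 has recording open through all of these steps.
3. Before the first session no event can be related to an intervention that has not been received, so nothing in that window can satisfy 8.4.1.
4. Section 2.3.1 nevertheless expects that distress or suicidal ideation may occur at the baseline questionnaires.
5. Recording is therefore open for a foreseen harm that cannot qualify. Sections 5.5.2 and 9.2 plan 226 enrolments, each with one baseline assessment: 226 × 1 = 226 patients at most. This counts exposure, not events.

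**Threshold**

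The closing phrase of the 8.4.2 list can be read in two ways.

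- *It governs the whole list.* Every SAE must then be directly due to the intervention. The definite grade in 8.4.3.2 fits easily, since it requires that "There is clear evidence to suggest a causal relationship, and other possible contributing factors can be ruled out". Whether a fatal or hospitalising event graded probable or possible also fits is not stated.
- *It governs only the last criterion* (medically significant and judged serious). A fatal, life-threatening or hospitalising condition then carries no relatedness test in 8.4.2 and could be an SAE without being an AE under 8.4.1.

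Neither reading agrees with 8.4.1. The sentence on important medical events does not settle the matter. It starts from something that is already an AE, so it inherits the intervention-only scope, and it is written for events that need not be fatal, life-threatening or hospitalising. Section 9.4.4 plans SAEs by relationship, which suggests that more than one grade was expected among SAEs.

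**The case against.** Several counter-arguments are sound.

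- Restricting AEs to related events is a deliberate choice for a minimal-risk psychological trial. It is not challenged here.
- Section 8.4.3.2 does not redefine an AE. Its heading refers to the intervention, and it grades events that already meet 8.4.1. Section 8.4.4 sets a time window, not a causal scope. This stands, but it confirms that 8.4.1 governs, and 8.4.1 leaves out what 2.3.1 foresees.
- The possible grade is broad. It needs only some evidence, such as reasonable timing, and allows for other contributing factors. Much sustained deterioration at the 2-, 3-, 6- and 9-month assessments follows the sessions and may already qualify. This also stands, and it is why the baseline questionnaires are the clear case. Transient distress is excluded in any event, because 8.4.1 requires a sustained reaction.
- Patient protection does not hang on the label. Section 2.3.3 provides a real-time alert on the Beck scale, psychologist risk assessment and a separate distress pathway. These are clinical responses, however, and do not place an event in the AE or SAE record. The unanticipated-problem route in 8.5.1 requires, among other things, that the event be unexpected. That is harder to meet for harms already listed as known risks, although unexpected severity or frequency could qualify.

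A reader might infer that the three sites will classify the same event differently. The text gives only weak support for this. Site teams manage AE data, so first recording could vary, but 8.4.3.2 gives causality grading to the PI, 8.4.5 and 8.4.6 have SAEs evaluated in consultation with the PI, and 9.5.7 has the PI review AEs monthly.

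**Conclusion.** The point holds as a mismatch of scope and threshold between the safety definitions and the sections around them. On a literal reading, a sustained assessment reaction is outside 8.4.1, most clearly at baseline in up to 226 patients, and the SAE status of a serious event graded probable or possible is undetermined. The number of events affected is unknown and cannot be computed from the protocol. The primary result is unaffected. The conclusion assumes that staff apply 8.4.1 and 8.4.2 as written. Staff who take their lead from 8.4.3.2 may record assessment reactions anyway.

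Two stronger readings are not supported. A reader might infer that only definitely related events can be SAEs. The documents do not say so: the phrase in 8.4.2 is not an 8.4.3.2 grade, and directly may simply mean not indirectly. The wording is ambiguous rather than demonstrably restrictive. A reader might also treat every follow-up questionnaire as falling in the gap, but most of these come after sessions, where the possible grade may already apply.

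This merits consideration at the next amendment. It goes somewhat beyond an editorial point, because the definition decides what is reported to the NIH and IRB.

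**What to change.** 1. In 8.4.1 and 8.4.2, widen the causal scope to *study intervention or study procedures, including assessments*.
2. In 8.4.2, replace the direct-causation phrase with *definitely, probably, or possibly related to*, placed so that it plainly applies to every seriousness criterion.
3. In 9.4.4, use the same scope for relationship in the AE and SAE summaries.

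The related-only approach and the requirement that a reaction be sustained both stay. The cost is a wording amendment to three sections and slightly more AEs and SAEs to evaluate and report.
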